Physical Exercise Training to Enhance Executive and Social Functions

May 17th, 2021

Background

Executive function and social functioning

Executive functions (EF) refer to goal-directed cognitive processes consisting of three major components including cognitive flexibility (mental flexibility), inhibition (inhibitory control) and working memory (Diamond, 2013). These components interact with each other and play a crucial role in a range of life outcomes including mental and physical health (Barch, 2005; Miller, Barnes, & Beaver, 2011), school and job success (Bailey, 2007; Duncan et al., 2007) and marital harmony (Eakin et al., 2004). In addition, higher EF is associated with better problem solving, reasoning and planning skills (Diamond, 2013) as well as social functions.

Relationship between executive and social function and autism spectrum disorder

Autism spectrum disorder (ASD) is a neurodevelopmental disorder characterised by social communication and interaction impairments, as well as restricted and repetitive patterns of behavior (American Psychiatric Association, 2013). Individuals with ASD have EF impairments which are linked to the restricted and repetitive behaviors that characterise this condition (Robinson et al., 2009). The prevalence of ASD is increasing with as many as 1 in 68 individuals (CDC, 2018), which further augments the burden to the ASD individuals, their families and society (Baron-Cohen et al., 2009; World Health Organization, 2005a). Hence, it is essential to investigate the underlying mechanism of ASD and design a cost-effective training that can be widely adopted in the community to reduce impairments arising from ASD symptoms.

Importantly, ASD traits occur on a continuum, and increasingly there is recognition of a broader autism phenotype (BAP) (e.g., see Dawson et al., 2002) in those that show sub-clinical symptoms. Similarly, these individuals also show impairments in executive function (e.g., Hill, 2004) and social functions, making this group an important target for the development and implementation of interventions. As such, we can deliver appropriate training at an earlier stage to prevent associated impairments in those with ASD traits. Therefore, instead of ASD, the present study examines the individuals with BAP.

The role of physical exercise on executive and social function in autistic individuals

Given EF impairments along with social function deficits are found in the sub-clinical individuals with BAP (Hill, 2004), is the training pertaining to ASD applicable to these individuals? In prior literature, physical exercise (PE) has been proved to enhance EF (Best, 2010) and social functions (Sowa & Meulenbroek, 2012). For instance, regular PE can enhance cerebral blood flow and increase the formation of new blood vessels in a number of brain regions that are involved in EF and social functions (e.g., Colcombe & Kramer, 2003). More specifically, PE is shown to enhance the performance of EF in healthy children and pre-adolescents (Best, 2010) and those with ASD (Lang et al., 2010). For example, Lang et al. (2010) and Lochbaum and Crews (2003) found that PE including jogging significantly decreased the repetitive and off-task behaviors and the level of aggression in individuals with ASD. Nevertheless, although PE is shown to be beneficial to reduce the symptoms and EF as well as social impairments in ASD, whether it produces the same positive outcomes on enhancing EF and social functions in the non-clinical population remains to be answered.

To address the research questions listed above, this proposed study aims to investigate whether PE training enhances the EF and social functions in the adolescents with BAP.

Research plan and methodology

Participants

To detect possible differences between the means of the primary measure with a power of 80%, eighty adolescents from secondary schools in Hong Kong and Australia will be recruited in this study (Hopkins et al., 2009). Written informed consent will be obtained from all participants. For participants who are below 18 years old, the consent from their parents or guardians will be obtained. Based on their self-reported autistic traits measured by Autism- Spectrum Quotient- Adolescent Version (details listed below), they will be categorized into two groups: 1) typically developing group (low ASD traits) and 2) BAP group (high ASD traits). To be included in the study, they must meet the following criteria: a) age ranges from 7 to 20; b) studying at one of the primary and secondary schools in Hong Kong; c) have never been diagnosed with ASD or any other disorder listed in the Fifth Edition of *Diagnostic and Statistical Manual of Mental Disorders* (DSM-V); and d) are not currently under any psychiatric medications or therapies.

Randomization. This study consists of a double-blind, and randomized controlled trial (RCT). After obtaining the informed consent, participants will be randomized into two conditions (1. physical exercise (PE) training group or 2. control group) using urn randomization, a covariate adaptive randomization method. A trained research assistant or a fitness trainer will be responsible to monitor and ensure the safety of the training process.

Physical exercise training. The PE training will adapt the exercise training employed by Lochbaum & Crews (2003) and Nicholson et al. (2011) since they targeted adolescents with ASD and the protocol of training can easily be replicated. The entire PE training lasts for six weeks and participants need to participate in a total of 12 sessions. In each session, every participant will be trained to run for 30 minutes on a treadmill. According to Exercise and Sports Science Australia (ESSA) exercise intensity guidelines, the intensity of running is suggested to be moderate and vigorous (alternating between the two) in this proposed study.

Control group. Participating adolescents in the control group will not receive any treatments. They are considered as waitlist controls.

Measures

The following self-reported measures will be administered at the baseline, post-training and 1-year follow-up.

Demographics. A simple demographic questionnaire will be used to gather participants personal information, including age, gender, current medication or therapy, and medical history of the participant and his/her family members. Besides, the blood pressure and heart rate of the participants will be assessed by electrocardiogram.

Autistic traits. The Autism-Spectrum Quotient-Adolescent Version (AQ-Adolescent; Baron-Cohen et al., 2006) and related self-report scales will be used to measure ASD traits. The AQ- adolescent is a self-report questionnaire comprising of 50 items assessing five areas, namely social, attention switching, attention to detail, communication and imagination. Participants will be asked to rate each item on a four-point Likert scale. The AQ-Adolescent received an excellent test-retest reliability ($r = .92$; Baron-Cohen et al., 2006) and a good internal consistency ($\alpha = .88$, Sonié et al., 2013).

Executive functions and social functions. EF and social functions will be measured using the Cambridge Neuropsychological Test Automated Battery (CANTAB). The CANTAB is a computerized test battery targeting multiple neuropsychological functions that has been validated in different cultures (De Luca et al., 2003). This battery includes Reaction Time, Paired Associates Learning, Spatial Working Memory, One Touch Stockings of Cambridge, Multitasking Test, and Emotion Recognition Task. Besides

the CANTAB, participant's psychological well-being including resilience and mental health will be measured.

Implications

Although the benefits of physical exercise have been studied in the ASD, BAP is under studied in prior literature. This proposed study will extend from the current literature to investigate the non-clinical group who have autistic traits with a longitudinal and randomized controlled trial design (RCT). The findings of this proposed study have multiple levels of significance and implications. For instance, if the hypotheses are supported, the PE training which is more cost-effective than psychotherapy in treating EF and social functioning deficits and associated impairments can be promoted to school settings. Ultimately, it can be incorporated to the curriculum of the primary and secondary schools to reduce BAP and associated impairments in the adolescents. Secondly, by examining those with sub-clinical symptoms, this research will contribute to early trainings approaches for the condition. Lastly, this proposed study can also help promote physical activities among adolescents which can further decrease mental and health issues in Hong Kong (MacDonald et al. 2011).

References

Alvarez, J. A., & Emory, E. (2006). Executive function and the frontal lobes: A meta-analytic review. *Neuropsychology Review*, 16(1), 17–42. doi:10.1007/s11065-006-9002-x

American Psychological Association. (2013). *Diagnostic and statistical manual of mental disorders*. Washington, DC: Author.

Anderson, S. W., Bechara, A., Damasio, H., Tranel, D., & Damasio, A. R. (1999). Impairment of social and moral behavior related to early damage in human prefrontal cortex. *Nature Neuroscience*, 2(11), 1032.

Bailey, C. E. (2007). Cognitive accuracy and intelligent executive function in the brain and in business. *Annals of the New York Academy of Sciences*, 1118, 122–141. doi:10.1196/annals.1412.011

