# **Physical Exercise Training to Enhance Executive and Social Functions**

**May 17th, 2021**

## **Statistical Analysis Plan and Preliminary Results**

**Hypothesis:** PE is predicted to be effective in reducing the EF and social impairments in these adolescents.

**Statistical Analysis:** Repeated measure ANOVA using SPSS ( is a software package used for interactive, or batched, statistical analysis) are performed to test the effectiveness of PE on social functions and EF in low and high autistic groups.

**Preliminary Results:** Reduced aggression for both autistic groups was found in the intervention when compared to control. Worse empathy in the intervention group when compared to the controls in both autistic groups.

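### The autism-trait score is analysed as low versus high with no cut-off, group size or defining visit; a continuous baseline-AQ-by-arm term would be more informative and would close the open choice of split

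*Protocol*

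**What the plan says.** The protocol's Background states that "ASD traits occur on a continuum". Under Participants, the AQ-Adolescent is used to form two groups: "they will be categorized into two groups: 1) typically developing group (low ASD traits) and 2) BAP group (high ASD traits"). The four inclusion criteria that follow contain no AQ threshold. No cut-off score, percentile, norm, quota or expected number per group appears in either document.

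Under Measures, the AQ-Adolescent has 50 items ("Participants will be asked to rate each item on a four-point Likert scale") and is given at baseline, post-training and one year. The visit that assigns the group is not named. Under Randomization, arms are allocated "using urn randomization, a covariate adaptive randomization method", but the covariates are not listed, so AQ group is not shown to be one of them.

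The SAP plans repeated-measures ANOVA to test the "effectiveness of PE on social functions and EF in low and high autistic groups". It names neither an interaction term nor a model using the AQ score itself. Its Preliminary Results paragraph already reports aggression and empathy findings for both trait groups, without saying how they were split.

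**The concern.** The study aim concerns adolescents with BAP, so the split decides who the target population is and how many of the 80 belong to it. Three things follow.

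- The BAP group has no defined size. A cut near the top of the range would leave few such participants per arm.
- Reducing a graded score to two labels usually weakens the comparison of the exercise effect across trait levels.
- With by-group results in hand and no written rule, a later reader cannot tell whether the split was fixed in advance. Trying several cuts and keeping the best would inflate false positives.

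**Working it through.** **Inputs from the documents.** N = 80 ("eighty adolescents from secondary schools in Hong Kong and Australia will be recruited in this study"); two arms; power from the sizing sentence, "To detect possible differences between the means of the primary measure with a power of 80" per cent. **Assumed, because not stated:** 1:1 allocation, two-sided 5% test, SD 1, no dropout, and one outcome value per participant (in a repeated-measures model the corresponding term is arm by visit by AQ).

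**1. The plan's own figure.** With no effect size, SD or alpha given, N = 80 can only be inverted. d = (1.960 + 0.842) × √(2/40) = 0.63 SD for all 80 participants. An effect of 0.63 returns N = 80; an effect of 0.5 would need 126.

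**2. What an undefined BAP group means for size.** The same formula, with n per arm inside the BAP group:

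| BAP participants | n per arm | Detectable d at 80% power | Power at d = 0.63 |
|---|---|---|---|
| 40 (50%) | 20 | 0.89 | 51% |
| 24 (30%) | 12 | 1.14 | 34% |
| 16 (20%) | 8 | 1.40 | 24% |

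The t distribution gives 0.91, 1.20 and 1.51.

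**3. Information on the arm-by-AQ interaction.** For a normal AQ and a linear moderating effect, a split that labels a share p as high keeps φ(z)²/[p(1−p)], where z is the cut on the standard normal scale.
- p = 0.5: 0.3989²/0.25 = 0.637, a loss of 36% (80 × 0.637 = 51 effective participants).
- p = 0.2: 0.2800²/0.16 = 0.490, a loss of 51%.

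Simulated median-split losses for other shapes: 25% for uniform AQ; 19% to 32% for two-peaked AQ; 41% to 52% for skewed or heavy-tailed AQ. If only the outer quarters or thirds of a normal AQ were recruited, the loss would be 13% to 19%, but the inclusion criteria describe no such selection. If the exercise effect truly steps at the cut, the loss is nil.

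**4. The exercise effect among high-trait participants.** Under the same assumptions, compare a continuous model evaluated at the high group's mean AQ, m = φ(z)/p, with the split estimate.
- Median split: m² = (0.3989/0.5)² = 0.637. Variances are (4/80)(1 + 0.637) = 0.082 and 4/40 = 0.100. The ratio is 0.82, a loss of 18%.
- Top 20%: m² = (0.2800/0.2)² = 1.96. Variances are (4/80)(2.96) = 0.148 and 4/16 = 0.250. The ratio is 0.59, a loss of 41%.

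**5. Illustrative interaction power.** Simulated with N = 80, residual SD 1 and normal AQ. The slope is the assumed change in exercise effect per SD of AQ; the AQ main effect is also assumed.

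| Slope | AQ main effect | Continuous | Median split | Top 20% |
|---|---|---|---|---|
| 0.65 | 0 | 79% | 58% | 45% |
| 0.65 | 0.3 | 79% | 54% | 40% |
| 0.3 | 0 | 26% | 18% | 15% |
| 0.3 | 0.3 | 25% | 17% | 13% |

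**6. Cost of an open cut.** With no true effect, taking the best of five cuts (top 50, 40, 33, 25 and 20%) rejects the interaction in about 13% to 14% of simulated trials instead of 5%.

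**The case against.** The strongest case on the other side has four parts.

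**The loss figures depend on shape.** A reader might infer that any split discards at least 36%. The documents do not support this: they give neither the AQ distribution nor the form of moderation, and plausible alternatives lose less or nothing. This stands, so the 36% is conditional.

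**The hypothesis is about benefit in these adolescents, and the SAP names no interaction.** This also stands. For the effect among high-trait participants, the loss at a median split is 18%, half the interaction figure. Nor does any of this touch the overall comparison of exercise with control.

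**A slope of 0.65 is large.** It means the exercise effect differs by 1.3 SD between AQ values one SD either side of the mean. At 0.3 no version of the analysis has useful power. This stands: the continuous term is the better use of the data, but it does not make 80 participants enough for a modest interaction.

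**A baseline split may well have existed.** Categorisation is described before randomisation, and the preliminary findings run the same way in both groups, so no interaction is being claimed. A reader might infer from the reported results that the cut was picked to suit them. The documents do not show that; they show only that no rule was written down. Similarly, the protocol's statement that "The AQ-Adolescent received an excellent test-retest reliability" (r = .92) does not favour either method by itself, because measurement error weakens a continuous term as well as a split.

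None of this supplies the missing cut-off, group size or defining visit, or gives a reason for preferring two groups to the score.

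**Conclusion.** The concern holds and is worth acting on before further analysis. The plan splits a trait that it describes as continuous, leaves the split undefined, and reports by-group results alongside. Given a roughly normal AQ and linear moderation, the split costs about 36% (median) to 51% (top 20%) of the information on the interaction. The corresponding loss for the exercise effect in high-trait participants at a median split is about 18%. Across other AQ shapes, the median-split loss on the interaction runs from about 19% to 52%, with no loss under a true step. The power figures illustrate assumed slopes and are not predictions for this trial. The 13% to 14% error rate is what an unrecorded choice among five cuts would cost; there is no evidence that such a choice was made.

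**What to change.** In the SAP:

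- Make baseline AQ total, as a continuous score, by arm the main moderator analysis, with one quadratic term as a linearity check.
- Use the baseline AQ only.
- Report the exercise effect with its 95% CI at prespecified AQ values. Include one BAP-defining baseline value, with its source, fixed before any further analysis. Sample percentiles alone are not enough, because they shift with who enrols and do not define BAP.
- Report how many participants in each arm lie above that value.
- Keep the low/high split, at that same value, as a secondary display, and label the by-group results already reported as exploratory.

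The AQ is already collected, so the cost is SAP wording. The downside is that a linear AQ term is assumed and the simple two-group headline becomes secondary.

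### The protocol calls the trial double-blind, but treadmill training against an untreated waitlist cannot be blind to participants or trainers, and no blinded party is named

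*Protocol*

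**What the plan says.** The protocol mentions blinding once, under Randomization: "This study consists of a double-blind, and randomized controlled trial (RCT". It does not say who is blinded.

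The same part of the protocol describes the arms:

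- Exercise arm, 12 sessions over six weeks: "In each session, every participant will be trained to run for 30 minutes on a treadmill". Supervision: "A trained research assistant or a fitness trainer will be responsible to monitor and ensure the safety of the training process".
- Control arm: "Participating adolescents in the control group will not receive any treatments. They are considered as waitlist controls".

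On outcomes, the Measures section opens with "The following self-reported measures will be administered at the baseline, post-training and 1-year follow-up". Under Autistic traits, the AQ-Adolescent and "related self-report scales will be used to measure ASD traits". Under Executive functions and social functions, "EF and social functions will be measured using the Cambridge Neuropsychological Test Automated Battery (CANTAB"), and the protocol adds that the participant's "psychological well-being including resilience and mental health will be measured", without naming an instrument or rater.

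The SAP says nothing about blinding. Its Preliminary Results section gives two between-arm findings, lower aggression and poorer empathy under exercise than under control, and names no instrument or rater for either.

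**The concern.** Double-blind tells a reader that knowledge of the arm has been removed as an explanation for a difference between arms. Here it has not been. An adolescent knows whether they have been running on a treadmill for six weeks or waiting, and the person supervising the session knows too.

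For a self-reported outcome the participant is also the assessor. Those in the exercise arm may report improvement because they expect it, and those on the waitlist may report less well because they are disappointed. A reader who relies on the label could treat both mechanisms as excluded. This applies to the AQ-Adolescent and its companion scales, and to any of resilience, mental health, aggression or empathy that are self-reported. The protocol's Implications section looks ahead to adoption of the training in schools if the hypotheses are supported, so the comparisons may be acted on.

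**Working it through.** **1. Is the label consistent with the design?** The documents state no figure on blinding to reproduce, so this part is a comparison of texts.

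| Party | What the documents say | Can the party be blind as described? |
|---|---|---|
| Participants | 12 treadmill sessions, or no treatment on a waitlist; no sham or attention control | No |
| Session supervisors | A research assistant or fitness trainer monitors the training | No |
| CANTAB administrators | Not mentioned in relation to blinding | Possible, not stated |
| Data handlers, analyst | Not mentioned in relation to blinding | Possible, not stated |

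No reading of the documents yields two named blinded parties.

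**2. Which outcomes are exposed?**

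- AQ-Adolescent and related scales: explicitly self-report, so the rater is unblinded.
- Resilience and mental health: rater not stated. The opening line of Measures suggests self-report, but the same heading also covers CANTAB and heart-rate measurement, so it does not settle the matter.
- Aggression and empathy: rater not stated. Empathy may come from a performance task, such as the CANTAB Emotion Recognition Task or the eyes task in Appendix 1.
- CANTAB: computerised performance, so less open to reporting bias, although effort can still depend on knowing the arm.

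**3. Illustration of what a reporting bias would do.** All of the following are assumptions: no true effect; 40 per arm (80 in total, split equally); three visits; no dropout; SD 1; compound symmetry with within-person correlation r; an arm-by-time F test at 5%; and a bias of b SD that is absent at baseline and equally large post-training and at 1 year. The SAP names only repeated-measures ANOVA, so the arm-by-time test is one reading of it.

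The arm-difference profile is (0, b, b). Its mean is 2b/3, so the centred profile is c = (−2b/3, b/3, b/3), and Σ(c/2)² = (1/4)(6b²/9) = b²/6.

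Noncentrality = 2n·Σ(c/2)²/(1−r) = 80·(b²/6)/(1−r) = 13.33·b²/(1−r), with 2 and 2·(80−2) = 156 degrees of freedom.

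| b | r | Noncentrality | Rejection rate | Simulated (40,000 runs) |
|---|---|---|---|---|
| 0.1 | 0.3 | 0.190 | 0.064 | 0.064 |
| 0.1 | 0.5 | 0.267 | 0.070 | 0.071 |
| 0.1 | 0.7 | 0.444 | 0.084 | 0.082 |
| 0.3 | 0.3 | 1.714 | 0.195 | 0.195 |
| 0.3 | 0.5 | 2.400 | 0.260 | 0.260 |
| 0.3 | 0.7 | 4.000 | 0.408 | 0.406 |

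With b = 0 the simulation gives 0.051, 0.048 and 0.049, as it should. Adding the SAP's low/high trait factor (error df 2·(80−4) = 152) changes no rate by more than 0.001.

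A cruder check is a two-sided z-test at one visit. The standard error is √(2/40) = 0.224, and the rejection rate is Φ(b/0.224 − 1.96) + Φ(−b/0.224 − 1.96). This gives 7.3% at b = 0.1 and 26.9% at b = 0.3, the same order of size.

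**The case against.** The strongest reply is about consequence. The SAP's hypothesis and analysis concern executive and social functions, which the protocol measures with CANTAB, the outcome least open to reporting bias. The AQ-Adolescent is used to sort participants into trait groups, and neither document calls it an efficacy outcome. No self-reported arm difference is shown to exist: the raters for aggression and empathy are unknown, and poorer empathy under exercise runs against a simple favourable expectancy effect. The label also stands a few lines from the arm descriptions, so a careful reader will see the conflict, and the SAP never claims blinding. Finally, every driver of the illustration is assumed.

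Much of this stands, and it limits the point to self-reported comparisons. The documents do not establish bias in any reported result, and the illustration is not evidence about this trial. But none of it makes the label true. The AQ-Adolescent is given at all three visits, so arm comparisons on it are possible. The direction of one result does not show that participants were blind. Readers who see only the label, or a report that repeats it, have no nearby arm description to correct it.

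**Conclusion.** The concern holds. The double-blind label contradicts the protocol's own description of the arms for participants and trainers, and it is undefined for anyone else. That conclusion rests on the text alone, with high confidence and no numerical assumption.

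The consequence is narrower. Self-reported between-arm differences could be given more trust than an open-label design supports; CANTAB results are less affected. The size cannot be estimated, because the documents give neither the amount nor the direction of any bias, nor the correlation between visits, allocation ratio or dropout. On the assumptions set out above, a 0.1 SD bias hardly matters, while a 0.3 SD bias would raise the 5% error rate roughly four- to eightfold (0.195/0.05 = 3.9; 0.408/0.05 = 8.2). The label should be corrected, but the planned analysis does not depend on it.

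**What to change.** 1. In the protocol, replace the double-blind label with a statement that the trial is open-label for participants and trainers. Add the same statement to the SAP, which is silent, and use it in reports.
2. State who, if anyone, was blinded. Claim blinding of CANTAB administrators or the analyst only if it was actually in place.
3. Mark every self-reported between-arm comparison as unblinded when it is reported and interpreted. To make that possible, name the instrument and rater for aggression, empathy, resilience and mental health. These details would be needed under any blinding scheme.

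No outcome is re-ranked and no analysis changes. The cost is wording only, with no new data, staff or procedures, and it can be done although preliminary results exist. The price is a less favourable design label. The change does not remove any bias; it tells the reader where bias is possible.

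### Allocation is covariate-adaptive, but the SAP's ANOVA carries no baseline variable beyond the low/high trait group; if other urn factors predict the tested outcome, a between-arm comparison loses power

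*Protocol*

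**What the plan says.** **Allocation.** The protocol (Research plan and methodology, Randomization) says that "participants will be randomized into two conditions", PE training or waitlist control, "using urn randomization, a covariate adaptive randomization method". It names no balancing covariate and gives no urn parameters. It places randomisation after consent and does not say which variables have been recorded by then.

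**Analysis.** The SAP's Statistical Analysis paragraph is the whole plan: "Repeated measure ANOVA using SPSS", and these analyses "are performed to test the effectiveness of PE on social functions and EF in low and high autistic groups". It lists no model terms, covariates, tested contrast or significance level. Trait group is the only baseline variable mentioned. Whether it enters as a factor or defines separate analyses is not stated, nor whether it is one of the urn covariates.

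**Setting.** The Participants section gives an eligible "age ranges from 7 to 20" and says that "eighty adolescents from secondary schools in Hong Kong and Australia will be recruited in this study". Measures are taken at baseline, post-training and 1 year. The executive and social outcomes are CANTAB tests.

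**The concern.** A covariate-adaptive urn makes the arms more alike on the chosen factors than simple randomisation would. If those factors also predict the outcome, the arm difference varies less from trial to trial. A model without the factors does not register this. It leaves their variance in the error term, so its standard error is larger than the true one, the test is conservative, and power is lower than in an adjusted analysis.

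The design needs at least one covariate, and the stated model can account for at most trait group. With eligibility from 7 to 20 years, age is a plausible further factor and a plausible predictor of cognitive test scores, although the documents state neither. In a trial of 80 people read across two trait groups, precision given up without need matters.

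**Working it through.** **Inputs from the documents.** Total N = 80 and 80% power (protocol, Participants); two conditions (Randomization); three visits (Measures).

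**Assumptions, because the documents are silent.** 40 per arm, two-sided 5%, no dropout, outcome SD = 1, an illustrative effect of 0.5 SD, share of outcome variance explained by the balanced factors R² = 0.1 to 0.3, and within-person correlation r = 0.6.

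**1. The plan's own figure.** The 80% power cannot be reproduced, because no effect size, SD or alpha is stated. Solving backwards, d = (1.96 + 0.842) × √(2/40) = 2.802 × 0.2236 = 0.63. N = 80 therefore implies an effect of about 0.63 SD. At 0.5 SD the power is lower, as step 2 shows.

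**2. Between-arm comparison at one visit.**
- Unadjusted SE = √(2/40) = 0.2236. Power = Φ(0.5/0.2236 − 1.96) = Φ(0.276) = 0.61.
- Adjusted SE = 0.2236 × √(1 − R²):

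| R² | adjusted SE | 0.5/SE | power = Φ(0.5/SE − 1.96) |
|---|---|---|---|
| 0.1 | 0.212 | 2.357 | 0.65 |
| 0.2 | 0.200 | 2.500 | 0.71 |
| 0.3 | 0.187 | 2.673 | 0.76 |

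Simulated urns come out slightly lower. With N = 80, an assumed urn on age band, sex and trait group, and outcome variance driven by age, power was about 60% unadjusted at each R². Adjusted power was 63-64% at R² = 0.1 and 74-75% at R² = 0.3. In one of these runs the unadjusted model already contained trait group, and the gap remained (60%, 60%, 60% against 64%, 69%, 74%).

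**3. Type I error of the unadjusted test.** Under perfect balance it is 2Φ(−1.96/√(1 − R²)), which gives 3.9%, 2.8% and 1.9% for R² = 0.1, 0.2 and 0.3. That is a limit that an urn does not reach, because it balances only approximately. Simulated urns gave about 3-5% (for example 4.6%, 4.4% and 3.1% in one run of 4,000 trials).

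**4. Arm-by-time contrast, baseline to post-training.**
- A factor that shifts a person's score equally at both visits drops out of the change score. In simulation, adding such factors gained nothing: 0.69-0.71 without them against 0.68-0.70 with them at 0.5 SD.
- Change-score variance = 2(1 − r) = 0.80. SE = √(0.80 × 2/40) = 0.200. Power = Φ(2.500 − 1.96) = 0.71.
- With the baseline score as a covariate, residual variance = 1 − r² = 0.64. SE = √(0.64 × 2/40) = 0.179. Power = Φ(2.795 − 1.96) = 0.80. Simulation gave 0.78-0.80.
- The same formulas give 0.53 against 0.68 at r = 0.4, and 0.94 against 0.96 at r = 0.8. The gain shrinks as the correlation rises.

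**The case against.** The strongest reply is that omission cannot be shown. The urn covariates are unnamed, and silence in a very short SAP is not a stated exclusion. Trait group is a natural urn factor; if it is the only one, the analysis already carries it. This stands in part. It makes the concern conditional, but as the plan is written any other urn factor is outside the model, and nothing commits the analyst to include it.

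The second reply is that the usual effectiveness test in a repeated-measures ANOVA is arm by time, where stable covariate effects cancel. This stands for factors that shift level only. The SAP does not say which contrast it tests, and over ages 7 to 20 with a 1-year follow-up a factor such as age may also predict change. The documents do not settle this.

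The third reply is that the error is conservative. This also stands: no bias and no excess of false positives follow. A reader might infer that power falls below the "with a power of 80"% that the protocol states. The documents do not support that. The loss is relative to an adjusted analysis, and at the implied effect of 0.63 SD, under perfect balance, the unadjusted test keeps at least 80%.

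**Conclusion.** The concern holds conditionally. The plan balances on covariates at allocation and does not commit to using them at analysis, apart from possibly trait group. If the remaining urn factors explain 10-30% of the variance of the tested outcome, a between-arm comparison at 0.5 SD has about 60% power instead of 63-74%, and its type I error is about 3-5%. For arm by time, level-only factors make no difference, and the available gain is from baseline adjustment, about 70% to 78-80% at r = 0.6.

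A reader might go further and conclude that the SAP's standard errors are too large and that power is certainly lost. The documents do not support this: they identify neither the balanced factors, nor their relation to the outcomes, nor the contrast to be tested. The figures rest on the assumed effect size, allocation ratio, alpha, R², correlation and form of urn.

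**What to change.** In the SAP, take the post-training and 1-year scores as the repeated outcomes. Enter the baseline score as a covariate and not also as a level of time. Include arm, trait group and every covariate used in the urn as fixed effects.

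In the protocol, name the urn covariates and state that they are recorded before allocation, including the AQ if trait group is one of them. If trait group is the only urn covariate, say so; the urn part of this point is then closed and the baseline adjustment remains worth making.

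The cost is a short rewrite of the SAP paragraph, one protocol sentence and a few degrees of freedom. No new data are needed, since the urn cannot run without these covariates and the baseline measures are already scheduled.
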